12.5 Pattern of Use Analyses

The pattern of use for GBCAs for MR (MRA/MRI) examination will be summarised for all GBCAs pooled, for non-Clariscan GBCAs pooled, and for all individual GBCAs administered during the study, including Clariscan. The overall pattern of use will be assessed based on summary data from a number of different centre, investigator, and patient-level variables as outlined below.

A qualitative analysis of these variables will be performed describing the overall pattern of use, referral pattern, and challenges in a radiological practice.

12.5.1 Centre Variables

The following summaries will be provided for the Centre Analysis Set:

- The average number of radiological procedures performed overall by centres during the recruitment period of the study.

- The average number of each type or radiological procedure (ultrasound, MR, CT scan, fluoroscopy, X-ray, SPECT, and PET examinations) performed by centres during the recruitment period of the study.
- The average percentage of each type of radiological procedure performed by centres during the recruitment period of the study as a proportion of the overall number of radiological procedures performed during the same period. The overall number of procedures from the centre will act as a denominator for the calculation of percentage and proportions of individual types of procedures.
- The average number of MR machines and staff (nurses and technicians) utilised by centres during the recruitment period of the study.

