The first 25 consecutive patients for which Clariscan is used and the first 25 consecutive patients for which any other GBCAs (all together 25 patients) is used, the images will be transferred for storage to allow a blinded image to read by an expert MR radiology panel to be performed in a future analysis. If the recruitment is less than 25 for either group, then the total images done for the group (Clariscan or GBCAs) during the recruitment period will be transferred. If a patient has repeat imaging for technical reasons and the image is not readable and has been repeated for same indication/reason, then the second readable image will be transferred for storage and analysis.

Investigator: the MR Radiologist; one investigator per centre.

Where a radiology team has multiple physicians involved in the patients' diagnosis and contrast media selections, the site investigators should appoint a single overarching Principal Investigator of the Centre.

Alternatively the study can be focused on a specific patient group under the responsibility of a single physician, as most appropriate to the local circumstances. Cumulative information

collected for the investigator at the end of the study refers to his/her practice during the recruitment period of the study (date of first patient and date of last patient recruitment).

Centre: the institution, hospital or private centre where the study investigator is practicing during the study and patients are recruited for the study from the centre. Cumulative data will be recorded on the eCRF for this centre for the period of recruitment (date of first patient and date of last patient recruitment).

[figure not shown]
Centres with electronic medical record (EMR), picture archiving and communication system (PACS), or any other system in place to collect the cumulative data at the end of the study and compatible for image transfer.

Table 1 Maximum Number of Patients Per Country

Country	Number of Centres	Maximum Number of Patients Allocated to Centres
Norway	1	200
Germany	2	300 + 600 = 900
Spain	3	500 x 2 + 200 = 1200
Italy	3	500 + 400 + 100 = 1000
Portugal	1	300
Poland	1	300 x 3 = 900
France	1	250

An overview of study procedures is presented in [Figure 1](#).

Figure 1 Study Diagram

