7 SELECTION AND WITHDRAWAL OF SUBJECTS

7.1 Procedures for Enrolment

After the start of the study all consecutive consenting adult and paediatric, male and female patients, undergoing MR procedures whose physician has made the decision to use GBCA as part of routine clinical practice will be enrolled. The enrolment of the total number of patients per centre will be limited to a defined number of patients for a centre (Table 1) with a maximum duration of recruitment of 3 months (month = 30days) from start date, i.e., first patient recruitment.

A subgroup of initial patients will be selected to transfer the anonymised images to GE Healthcare (GEHC) through AGMednet. The images will be archived at GEHC and analysed at a later date by an expert MR radiologist panel to assess the quality of images. The first 50 images will be transferred in a 1:1 ratio for Clariscan and other GBCAs, i.e., first consecutive 25 images (25 maximum or total recruited in 3 months) for Clariscan and other GBCAs. If sufficient number of images (25) for either group (Clariscan or other GBCAs) are not acquired in 3 months, the recruitment will stop at 3 months and all images will be transferred for the blinded read, the comparative analysis is not at centre level. All images will be pooled together for blinded image read by the expert panel.

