9.2 Post-Imaging Period

Safety measurements will be performed from GBCA administration until 7 days post-administration for AEs reported voluntarily by the patient. No follow-up safety assessment is required unless AEs are reported spontaneously by the patient or healthcare providers. However, AEs will be documented in line with the requirements applicable for use of medicines in general, irrespective of the documentation window.

The following information will be collected once at the end of the study:

- Customer satisfaction to be recorded by the local nurse/radiology technician once per centre for each GBCA used at the study centre, including generics
- Investigator information - cumulative numbers for the recruitment period (date of the first patient to date of last patient at the centre) of the study at the centre
- Centre information- cumulative numbers for the recruitment period (date of the first patient to date of last patient at the centre) of the study at the centre

The first 25 consecutive patients where Clariscan is used and the first 25 consecutive patients where any other GBCAs (all together 25 patients) is used, the images will be transferred for storage to allow a blinded image read by the expert MR radiology panel to be performed in a future analysis. If the recruitment is less than 25 for either group, then the total images done for the group (Clariscan or GBCAs) during the recruitment period will be transferred. If a patient has repeat imaging for technical reasons and the image is not readable and has been repeated for same indication/reason, then the second readable image will be transferred for storage and future analysis.

See Section 10.3 and the Study Schedule of Events Table ([Table 2](#)) for further details.

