10 PATTERN OF USE, EFFECTIVENESS, SAFETY, AND OTHER VARIABLES

10.1 Pattern of GBCA Use

[figure not shown]
The pattern of use for GBCAs including Clariscan for MR (MR angiography [MRA]/MRI) examination will be assessed based on the following variables:

1. The number of radiological procedures, including ultrasound, MR, computed tomography (CT) scan, fluoroscopy, X-ray, single-photon emission CT (SPECT), and positron emission tomography (PET) examinations, performed by the study centre during the recruitment period of the study. The number of procedures done by the study centre will be collected once in the study and will be used to assess the percentage and proportion of different procedures performed by the radiology department, including the percentage of MR procedures with or without GBCAs (total GBCAs and individual GBCA).
2. Number of MR machines and staff (nurses and technicians) will be recorded to assess the workload per MRI machine and staff.
3. The number of radiological procedures, including ultrasound, MR, CT scan, fluoroscopy, X-ray, SPECT, and PET examinations, reported by the investigator during the recruitment period of the study. The number of procedures done by the centre will be used to assess the percentage and proportion of different procedures performed by the investigator (radiologist), including the percentage of MR procedures with or without GBCAs (total GBCAs and individual GBCA).
4. Use of GBCAs – Total and individual GBCA (generic GBCA recorded as a separate entity) use as per indication, organ/system imaged, age, gender, body mass index (BMI; <18 is “underweight”, 18 to 25 is “normal”, 26 to 30 is “overweight”, 30 to 40 is “obese”, and >40 is “morbidly obese”), reason for use of GBCA and preference for a particular GBCA due to BMI.
5. Referral pattern for CE-MRI - Following information will be assessed:
 - a. Referring physician
 1. seniority (house officer or equivalent, registrar, consultant, super specialist)
 2. specialty (e.g., cardiologist oncologist)
 - b. The quality of referral will be assessed by the radiologist as follows:
 - 1 = not enough information
 - 2 = have all necessary information

3 = good full detailed information with clear question

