10.4.4 Cumulative Data

To understand the Pattern of Use mentioned in Section 10.1, the following data will be complete only at the end of recruitment period:

- **Investigator Information (recorded once at the completion of recruitment):**

This information will be cumulative and consist of only numerical values and will include all procedures performed by the investigator regardless of whether or not the patient agreed to enrol in the study. No information about the individual patients will be required. This information will act as a denominator for calculation of percentage and proportions.

- Total number of procedure performed during the recruitment period
- Number of MRI procedures (enhanced and non-enhanced) performed during the recruitment period
- Categories/number of other procedure performed during the recruitment period

- **Centre Information (recorded once at the completion of recruitment):**

This information will be cumulative and consist of only numerical and will include all procedures performed by the investigator regardless of whether or not the patient agreed to enrol in the study. No information about the individual patients will be required. This information will act as a denominator for calculation of percentage and proportions.

- Total number of procedures performed during the recruitment period
- Categories/number of other procedure performed during the recruitment period

- Equipment for imaging (MRI, CT, ultrasound, X-ray machines, gamma camera, PET, fluoroscopy)
- Staffing of radiology department (optional)

Addition information will be recorded as categories or descriptive text (collected once at the end of recruitment period for a study centre/institution):

- Decision maker in the department – this information will be about the healthcare providers or administrator who play active role in decision making for the radiology department. For example: (categories) radiologist, head of department, cardiologist, managers, pharmacist (optional).
- Three challenges in the department in order of priority, reported as free text.

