12.9 Sample Size Calculation

This is an observational study to understand the pattern of use of GBCAs use in CE-MR. The sample size is not based on statistical considerations, as the study does not formally test a hypothesis. Recruitment will be open for 3 months (90 days), with a cap on the maximum number of patients recruited by each centre (Table 1), and all consecutive patients who provide informed consent from the start of study (after Clariscan is on formulary in the study centre and available for routine clinical use) will be enrolled. Even if the centre has not enrolled the maximum number of patients allocated for that centre, recruitment will close at the end of the 90-day enrolment period regardless of the number of patients enrolled. It is anticipated that up to 5,400 patients from European countries where Clariscan has been launched will be enrolled. The maximum number of patients per country can be found in Table 1.

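### Centre and investigator procedure counts are averaged without a time unit over windows that close at each centre's cap, so for centres that reach the cap they do not reflect activity

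*Protocol*

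**What the plan says.** **Summary.** The first bullet of section 12.5.1 is "The average number of radiological procedures performed overall by centres during the recruitment period of the study". The next bullet does this for each type of procedure. Section 12.5.2 repeats both for investigators and adds average numbers of enhanced and non-enhanced procedures. None of these is stated per day, per month or over a common period.

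**Counting window.** Section 6.1 has the cumulative data recorded "for this centre for the period of recruitment (date of first patient and date of last patient recruitment", and section 9.2 agrees: "Centre information- cumulative numbers for the recruitment period (date of the first patient to date of last patient at the centre". The investigator data use the same window.

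**Stopping rule.** Section 12.9 states "Recruitment will be open for 3 months (90 days), with a cap on the maximum number of patients recruited by each centre". Section 7.1 says that enrolment "will be limited to a defined number of patients for a centre (Table 1) with a maximum duration of recruitment of 3 months". Table 1 sets centre caps from 100 (one Italian centre) to 600 (one German centre).

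**Workload and staffing.** Section 10.1, item 2 reads "Number of MR machines and staff (nurses and technicians) will be recorded to assess the workload per MRI machine and staff", and 12.5.1 plans an average of machines and staff. In the data list of 10.4.4 the matching entry is "Staffing of radiology department (optional").

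**The concern.** A count accumulates with time, and here the observation time differs by centre. It is set partly by a sponsor-assigned quota and partly by how fast the centre fills it. Averaging such counts mixes how busy a centre is with how long it was watched.

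Pattern of use is the primary objective, and the centre and investigator procedure numbers and the workload measure are items 1 to 3 of its variables in 10.1. A reader will take an average number of procedures per centre as a level of activity. If caps bind, two equally busy centres can show very different counts, and centres of very different activity can show the same one.

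Optional staffing is a separate matter. It does not cause the window problem, but it can leave the per-staff part of workload incomplete.

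**Working it through.** **The plan's own figure.** The only overall size stated is up to 5,400 patients. The Table 1 caps give 200 + 900 + 1,200 + 1,000 + 300 + 250 + 900 = 4,750 over the 14 centres of the synopsis, 650 fewer. That mismatch is a separate inconsistency and nothing below depends on it.

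**Inputs from the protocol.** Caps by centre: 100; 200 (two centres); 250; 300 (five); 400; 500 (three); 600. Maximum recruitment: 90 days.

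**Inputs not in the protocol (assumed, shown as a range).** Patients enrolled per day, *e*; radiological procedures per day, *a*.

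**Formulas.** Window = min(90, cap / *e*). Count = *a* × window. If the cap is reached, count = cap × (*a* / *e*), that is, the cap times procedures per enrolled patient.

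**When does the cap bind?** When *e* exceeds cap / 90: 100/90 = 1.1 per day, 300/90 = 3.3 per day, 600/90 = 6.7 per day.

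**Windows at a common enrolment rate in all 14 centres:**

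| Enrolled per day (assumed) | Centres reaching cap | Windows, days | Longest / shortest |
|---|---|---|---|
| 1 | 0 | all 90 | 1.0 |
| 2 | 1 | 50 to 90 | 1.8 |
| 3 | 4 | 33 to 90 | 2.7 |
| 5 | 10 | 20 to 90 | 4.5 |
| 7 | 14 | 14 to 86 | 6.0 |
| 10 | 14 | 10 to 60 | 6.0 |

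**Same activity, different counts.** With an assumed 300 procedures per day in every centre, raw counts run from 15,000 to 27,000 at 2 enrolled per day, from 6,000 to 27,000 at 5 per day, and from 3,000 to 18,000 at 10 per day. As a rate, every centre gives 300 × 30 = 9,000 per 30 days.

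**Different activity, same count.** Take a cap of 300 and let enrolment rise in proportion to activity:

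| Procedures per day | Enrolled per day | Window, days | Raw count | Per 30 days |
|---|---|---|---|---|
| 300 | 5 | 60 | 18,000 | 9,000 |
| 600 | 10 | 30 | 18,000 | 18,000 |
| 1,200 | 20 | 15 | 18,000 | 36,000 |

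A fourfold difference in activity vanishes from the raw count. Dividing by machines does not restore it: with two machines the figure is 9,000 per machine in each row.

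**What does not depend on the window.** The percentage of each procedure type divides by the total for the same period, so window length cancels within a centre. The number of MR machines is not a cumulative count.

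**The case against.** The strongest reply is that the counts serve mainly as denominators. Section 10.4.4 says so, 10.1 items 1 and 3 use them for percentages, and 6.2 asks what proportion of procedures are contrast-enhanced MR. Those percentages are sound. This stands and narrows the point to the bullets that average numbers of procedures. It does not remove it, because 12.5.1 and 12.5.2 list those averages as summaries in their own right.

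Second, the caps may seldom bind. Section 12.9 provides for centres that do not fill their allocation, and at 1 patient per day there is no distortion. Caps may also have been set to match expected throughput, which would make windows more alike; the protocol does not say. A reader might take the 6-fold range of caps as the expected distortion, but that needs all centres to cap at a common rate, and no accrual figure supports it.

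Third, a reader might infer that the busiest centres will show the lowest counts. With equal caps and enrolment proportional to activity, the count never falls as activity rises; capped centres tie. A reversal needs unequal caps or different ratios of procedures to enrolled patients. It is possible, but not shown.

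Fourth, no workload formula is given, and one with a time unit may sit in an analysis plan that is not shown. The criticism of workload therefore applies only if it is built on the raw counts. The window and the raw averages, by contrast, are fixed in the protocol itself.

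On staffing, 10.4.4 speaks of the radiology department and 10.1 of nurses and technicians, so the entries might be distinct. But 10.4.4 has no other staff entry, so the conflict remains. How many centres would leave it blank is unknown.

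**Conclusion.** The point holds for the average numbers of procedures (overall, by type, and enhanced or non-enhanced) in 12.5.1 and 12.5.2. For any centre that reaches its cap, the count reflects the quota and the procedures per enrolled patient rather than the level of activity. Averages that include such centres cannot be read as activity, nor can a workload figure derived from them. Centres that do not cap are counted over roughly 90 days and are comparable with one another.

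The size cannot be fixed from the protocol. Under a common enrolment rate it ranges from none at 1 per day to 6-fold at 7 per day or more. These rates are assumptions, and real centres will differ in both enrolment and activity.

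It would go too far to say that the pattern-of-use analysis as a whole measures time to cap: percentages, machine numbers and patient-level summaries are unaffected. Optional staffing is a distinct contradiction between 10.1 item 2 and 12.5.1 on one side and 10.4.4 on the other. The change is worth making because it makes a primary-objective summary interpretable at almost no cost.

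**What to change.** In 12.5.1 and 12.5.2, report the cumulative procedure counts per 30 days of each centre's window, as count / window in days × 30. Each centre's first- and last-patient dates already define the window. Show the window length beside each rate. Leave the percentage summaries as they are.

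In 10.1 item 2, express workload as MR examinations per machine, and per MR staff member, per unit time.

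Separately, either make the MR nurse and technician count mandatory in 10.4.4 or drop per-staff workload from 10.1 and the staff average from 12.5.1.

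The cost is revised wording, a minor extra calculation and, if per-staff workload is kept, one mandatory field per centre. No further patients are needed. A fixed 90-day count at every centre would also equalise the windows, but it changes data collection at centres that close early and is not needed.

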12.5.2 Investigator Variables

The following summaries will be provided for the Investigator Analysis Set:

- The average number of radiological procedures performed overall by investigators during the recruitment period of the study.
- The average number of each type or radiological procedure (ultrasound, MR, CT scan, fluoroscopy, X-ray, SPECT, and PET examinations) performed by investigators during the recruitment period of the study.
- The average percentage of each type of radiological procedure performed by investigators during the recruitment period of the study as a proportion of the overall number of radiological procedures performed during the same period. The overall number of procedures from the centre will act as a denominator for the calculation of percentage and proportions of individual types of procedures.
- The average number of enhanced and non-enhanced procedures performed by investigators during the recruitment period of the study.

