7.3 Exclusion Criteria

- Use of liver-specific GBCAs (Primovist and MultiHance when used for liver excretion properties).*

Note for exclusion criteria:

Please note if GBCAs are used off label in clinical practice for patients in indications not listed in the Summary of Product Characteristics (SPC), these will be reported as off label use.

*For liver-specific GBCAs used (where excretion by the hepatocytes is the mechanism as opposed to extracellular) no patient or procedure level data will be collected and these patients will also not be included in the subgroup of patients where image transfer will be done. There is no plan to do image assessment performed by liver-specific contrast medium as Clariscan does not have this indication and is not excreted by the liver. MultiHance, when used for liver excretion properties, will also not be included, but for all other indications it will be included for full data collection.

However, when reporting the overall number of MR procedures for the study centre and operating investigator, liver-specific agents will be reported in the cumulative data as the number of procedures done by liver-specific agents.

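### Investigator procedure percentages are set on the centre's total, and Protocol 10.4.4 mis-scopes the centre counts and omits MR counts that 10.1 needs

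*Protocol*

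**What the plan says.** **Denominator.** Protocol 12.5.2 defines the summary as "The average percentage of each type of radiological procedure performed by investigators during the recruitment period of the study as a proportion of the overall" count for that period, and adds "The overall number of procedures from the centre will act as a denominator for the calculation of percentage and proportions". The same sentence closes the matching bullet in 12.5.1 for centres, and the synopsis uses it once for both levels. Section 10.1 item 3 agrees: "The number of procedures done by the centre will be used to assess the percentage and proportion of different procedures performed by the investigator". Section 10.4.4, under Investigator Information, describes the investigator's own cumulative counts and says "This information will act as a denominator for calculation of percentage and proportions". It repeats that sentence under Centre Information.

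**Scope of the centre counts.** The Centre Information paragraph of 10.4.4 reads "This information will be cumulative and consist of only numerical and will include all procedures performed by the investigator". Section 6.1 has cumulative data recorded for the centre, and 10.1 item 1 concerns procedures performed by the study centre.

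**MR counts by contrast use.** Section 10.1 items 1 and 3 describe the procedure percentages for centre and investigator as "including the percentage of MR procedures with or without GBCAs (total GBCAs and individual GBCA"). In 10.4.4 the investigator list has MRI, enhanced and non-enhanced. The centre list has a total and the numbers of other procedure categories. Neither list has a line by individual GBCA. Section 7.3 says that "liver-specific agents will be reported in the cumulative data as the number of procedures done by liver-specific agents", but neither list repeats that item.

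**The concern.** A procedure mix tells the reader how a radiologist's work divides among modalities, so its parts must add to 100%. Dividing the investigator's counts by the centre's total gives another quantity: the fraction of the department's output that is this investigator's work of that type. It depends on department size and staffing as much as on practice, and averaging it across investigators blends the two.

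The centre-level wording adds a second difficulty. If some centres follow the literal text of 10.4.4 and others follow 6.1, the averages in 12.5.1 combine single-investigator totals with whole-department totals.

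The third difficulty is supply. The percentage of MR done with and without GBCA, and by agent, belongs to the pattern-of-use variables serving the only primary objective. Section 6.2 also wants to know what proportion of contrast-enhanced MR falls to the investigator and to the institution. The first needs MR counts by contrast use at both levels, and the second needs at least the enhanced count for the centre. Cumulative data are entered once, at completion of recruitment, so an item not on the list may not be asked for in time.

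**Working it through.** The protocol states no figure for these percentages, so there is none to reproduce. The check has one identity and two comparisons of text.

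**1. Effect of the denominator**

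For one investigator, let:
- T = the investigator's total procedures and M = the MR procedures among them (both listed in 10.4.4);
- C = the centre's total procedures;
- m = M/T, the MR share of the investigator's own work;
- s = T/C, the investigator's share of centre volume.

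On the investigator's base the MR percentage is M/T = m, and all types sum to T/T = 100%. On the centre base it is M/C = (M/T)(T/C) = m × s, and all types sum to T/C = s.

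The protocol gives no volumes, so s and m are assumptions:

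| s | m = 30% | m = 60% | m = 90% | Sum over all types |
|---|---|---|---|---|
| 0.05 | 1.5% | 3% | 4.5% | 5% |
| 0.10 | 3% | 6% | 9% | 10% |
| 0.25 | 7.5% | 15% | 22.5% | 25% |
| 0.50 | 15% | 30% | 45% | 50% |
| 1.00 | 30% | 60% | 90% | 100% |

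The bases agree only at s = 1. Averaging does not help: two investigators with the same 60% mix and s of 0.05 and 0.50 would be reported as 3% and 30%, with a mean of (3 + 30)/2 = 16.5%, which describes neither.

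**2. Scope of the centre total**

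Read literally, the Centre Information text makes C = T, hence s = 1. The investigator percentages would then sum to 100%, but only because the centre total had been replaced by the investigator's, and the centre table would no longer describe the centre. Read with 6.1 and 10.1 item 1, C is the department's total and the distortion in step 1 applies.

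**3. Counts needed against counts listed in 10.4.4**

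| Needed for 10.1 items 1 and 3 | Investigator list | Centre list |
|---|---|---|
| Total procedures | Yes | Yes, with the wording problem above |
| MR, enhanced and non-enhanced | Yes | Not listed |
| MR enhanced, by individual GBCA | Not listed | Not listed |
| MR with liver-specific agents | Promised in 7.3, not in the list | Promised in 7.3, not in the list |

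Section 12.5.2 summarises enhanced and non-enhanced procedures for investigators; 12.5.1 has no counterpart for centres.

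Patient-level data cannot fill the gap. GBCAs given to subjects are recorded by brand (8.1.2), but subjects are consenting patients (7.2.3) up to a cap per centre (Table 1), all chosen for contrast, with liver-specific use excluded (7.3). They contain no unenhanced examinations, and 10.4.4 itself wants cumulative counts that do not depend on enrolment.

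**The case against.** The strongest defence is that the centre denominator is deliberate. It appears in three places, 6.2 is interested in the proportion of contrast-enhanced MR done by investigator and institution, and 10.4.4 calls the investigator's counts a denominator without saying of which percentage. A share-of-centre measure may therefore have been meant. That possibility stands, but 10.1 item 3 and 12.5.2 describe a breakdown by procedure type, so the text has to say which quantity is intended. In either case the investigator's total and counts by type are collected, so both percentages can be computed and no data are lost on this point.

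On scope, the heading in 10.4.4 says Centre, the schedule of assessments has separate centre and investigator rows, and 6.1 is clear. The wording is probably carried over from the investigator paragraph, and many sites would read past it. That stands too: it is an editorial error, though one in the instruction that sites follow when they fill in the form.

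On the missing lines, a reader might infer that no form collects MR counts by contrast agent and that the percentages are lost. The documents do not support that. The eCRF is not shown, 7.3 commits to cumulative liver-specific counts, 10.4.4 lists enhanced and non-enhanced MRI for the investigator, and 10.4.4 says that it serves the variables in 10.1. Eligible centres must also hold the cumulative data electronically (7.2.1), so counts can be requested up to completion of recruitment. What remains is that the section defining the cumulative data does not list counts that 10.1 depends on.

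**Conclusion.** The point holds in three limited parts.

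- The investigator percentages are put on a base that does not yield a procedure mix, and 10.4.4 points to another base. The reported value is m × s instead of m. For an assumed s of 0.05 to 0.50, a 60% MR mix would be shown as 3% to 30%. Where one Principal Investigator stands for a whole radiology team, s may be nearer 1 and the distortion smaller.
- The Centre Information wording contradicts 6.1 and 10.1 item 1.
- Section 10.4.4 does not list enhanced and non-enhanced MR for the centre, or MR by individual GBCA at either level.

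A statistical analysis plan could settle the denominator, but it could not supply counts that centres were never asked to report.

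This does not make the primary objective unattainable. Patient-level use of each GBCA (10.1 item 4, 12.5.3) is unaffected, the study is descriptive, and the first part can be repaired from collected totals. It should be fixed because stated rules would misreport or fail to supply pattern-of-use variables, and correction is cheap.

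**What to change.** - In 10.1 item 3, 12.5.2 and the synopsis, use the investigator's own total as the denominator for the investigator's procedure mix. If a share of centre volume is also wanted, report it as a separate quantity with its own label.
- In 10.4.4, Centre Information, change the wording so that it covers all procedures performed by the centre.
- In both cumulative lists of 10.4.4, include MR non-enhanced, MR enhanced, and MR enhanced by GBCA, with liver-specific agents as their own line as 7.3 promises.
- Add the matching summaries to 12.5.1 and 12.5.2.
- Check the eCRF against the revised lists before centres complete their cumulative data.

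The cost is a protocol wording change and a few more numeric fields per centre, drawn from electronic records that centres must already have to be eligible. Extracting counts by agent is some extra work for sites, done once.
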